#### 10.4.2.2 Dexamethasone Dose Modification Guidelines

Guidelines for dexamethasone dose modifications and treatment are summarized in [Table 15](#).

Approved

**Table 15 Treatment Guidelines for Dexamethasone-Related Toxicity**

Body System	Symptom	Recommended Action
Gastrointestinal	Dyspepsia, gastric or duodenal ulcer, or gastritis Grade 1 or 2 (requiring medical management)	Continue dexamethasone at same dose and treat with therapeutic doses of H 2 blockers, or proton pump inhibitor. May consider adding sucralfate or other antiulcer treatment as clinically indicated. If symptoms persist despite above measures, decrease dexamethasone dose by 1 dose level.
Gastrointestinal	Dyspepsia, gastric or duodenal ulcer, or gastritis ≥ Grade 3 (requiring hospitalization or surgery)	Hold dexamethasone until symptoms return to baseline. Restart dexamethasone at 1 dose decrement along with concurrent therapy with H 2 blockers, sucralfate, or omeprazole. If symptoms persist despite above measures, discontinue dexamethasone permanently.
Gastrointestinal	Acute pancreatitis	Discontinue dexamethasone permanently.
General Disorders	Edema > Grade 3 (> 30% limb discrepancy in volume; gross deviation from normal anatomic contour; limiting self-care activities of daily living)	Hold dexamethasone until symptoms return to baseline. Administer diuretics as needed, and restart dexamethasone at 1 dose decrement; if edema persists despite above measures, decrease dose another level. Discontinue dexamethasone permanently if symptoms persist despite second reduction.
Psychiatric Disorders	Confusion or mood alteration ≥ Grade 2 (interfering with function ± interfering with activities of daily living)	Hold dexamethasone until symptoms return to baseline. Restart dexamethasone at 1 dose decrement. If symptoms persist despite above measures, reduce by another dose decrement.
Musculoskeletal	Muscle weakness ≥ Grade 2 (symptomatic and interfering with function ± interfering with activities of daily living)	Hold dexamethasone until symptoms return to baseline. Restart dexamethasone at 1 dose decrement. If weakness persists, decrease dose by 1 more dose level. Discontinue dexamethasone permanently if symptoms persist.
Metabolism and Nutrition Disorders	Hyperglycemia ≥ Grade 3 (fasting glucose > 250 mg/dL)	Hold dexamethasone until glucose is ≤ Grade 2 (< 250 mg/dL) and treat with insulin or other hypoglycemic agents as needed. If uncontrolled despite above measures, decrease dose by 1 dose level until ≤ Grade 2 (< 250 mg/dL)
All Other	Other nonhematologic toxicity ≥ Grade 3 felt related to dexamethasone	Hold dexamethasone dose. Resume at 1 dose decrement when toxicity has resolved to Grade 2 or less or to baseline. If toxicity recurs, hold dexamethasone dose until toxicity has resolved to Grade 2 or less or to baseline and resume dexamethasone dose by 1 more dose decrements. If toxicity recurs despite 2 dose decrements, discontinue dexamethasone permanently.

H2 = histamine 2 blocker.

Approved

## 10.5 DEFINITION OF DOSE-LIMITING TOXICITY

During this study, assessment of DLTs will occur during the 28-day period of Cycle 1 combination therapy. For the purposes of this study, a DLT is defined as any of the study drug-related events listed below occurring within the 4 weeks after the first dose of combination therapy. Study drug-related is defined as a reasonable likelihood of clinical causality based on time of event, biology, dechallenge improvement and that the AE was not likely explained by the subject's clinical state, underlying disease, concomitant medication, or study/nonstudy procedure.

- Any toxicity requiring a dose reduction or requiring that a dose of oprozomib or pomalidomide be held in Cycle 1 that does not meet the criteria for DLT will be discussed by the CSRC to determine whether the subject should be considered evaluable for DLT determination. If it is determined that the subject is not evaluable for DLT, the subject will be replaced.
- A delay in ability to receive Day 1 dose of Cycle 2 due to a hematologic or nonhematologic drug-related toxicity persisting beyond 14 days from Cycle 1 Day 28 will be considered a DLT
- For a nonhematologic DLT, any  $\geq$  Grade 3 toxicity will be considered a DLT with exceptions as described below:
  - Grade 3 asymptomatic electrolyte abnormalities will not be considered a DLT
  - Asymptomatic Grade 3 hypophosphatemia lasting less than 24 hours will not be considered a DLT
  - Grade 3 nausea and vomiting will not be considered a DLT unless persisting longer than 3 days despite optimal supportive care, which at a minimum must include a 5-hydroxytryptamine type-3 (5-HT3) antagonist and aprepitant
  - Grade 3 diarrhea will not be considered a DLT unless persisting longer than 3 days despite optimal supportive care, which at a minimum must include loperamide (Imodium) and atropine diphenoxylate (Lomotil)
  - Grade 3 fatigue lasting < 14 days is not considered a DLT
  - $\geq$  Grade 3 hyperglycemia or toxicity attributed to dexamethasone is not considered a DLT (see dose reduction guidelines for dexamethasone in [Section 10.4.1](#))
  - $\geq$  Grade 3 rash attributed specifically to pomalidomide is not to be considered a DLT

Approved

CONFIDENTIAL

- Hematologic DLTs consist of the following:
  - Grade 4 neutropenia:
    - Absolute neutrophil count (ANC)  $< 0.5 \times 10^9/L$  lasting  $\geq 7$  days despite adequate growth factor support (eg, G-CSF)
    - Febrile neutropenia: Any single temperature  $\geq 38.3^\circ C$  or a sustained temperature of  $\geq 38.0^\circ C$  for over 1 hour with  $\geq$  Grade 3 neutropenia (ANC  $< 1.0 \times 10^9/L$ )
  - Thrombocytopenia:
    - Grade 4 lasting  $\geq 7$  days, or
    - Grade 4 lasting  $< 7$  days with Grade 2 clinically significant bleeding or  $< 10,000$  platelets requiring platelet transfusion, or
    - Grade 3 with clinically significant bleeding or requiring platelet transfusion.

Note: Grade 4 anemia is not considered a DLT

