## 5.1 DOSE-ESCALATION AND DOSE-EXPANSION PORTIONS OF THE STUDY

In **this** study, the safety, MTD, PK/PDn, and RP3D of oprozomib when given in combination with pomalidomide and dexamethasone will be assessed using a standard 3 + 3 dose-escalation design. For each of the 2 schedules being studied, groups of 3 to 6 subjects will be enrolled into dose-escalation cohorts. As long as fewer than 33% of subjects experience a DLT in a given cohort, escalation will continue by 30-mg increments of oprozomib onto the next designated cohort(s). A minimum of 6 subjects must be treated at the MTD to establish the dose as the MTD. If the starting dose of oprozomib cannot be safely administered with the labeled pomalidomide dose or at sponsor discretion, then up to 2 possible alternative dose-escalation paths for oprozomib with lower pomalidomide doses will be explored (See tables below for primary and alternative dose-escalation paths). Dose escalation will continue until until sponsor discretion, the maximum planned dose of pomalidomide is reached, or  $\geq 2$  DLTs occur in a cohort, whichever occurs first. The prior cohort will be expanded to at least 6 subjects if not previously done to establish it as the MTD. There may be more than 1 MTD of oprozomib if more than 1 dose level of pomalidomide is studied. The MTD for oprozomib associated with each dose level of pomalidomide assessed will be the dose level where  $< 2$  DLTs in 6 subjects are observed.

There is no planned maximum dose of oprozomib to be evaluated as it is being added to the FDA-approved regimen of pomalidomide/dexamethasone, however, this could be imposed at any time during the course of the study, based on sponsor discretion. The starting dose of oprozomib for the 5/14 schedule is 150 mg, 3 dose levels below the established single-agent MTD of 240 mg. The starting dose of oprozomib for the 2/7 schedule is 210 mg, 3 dose levels below the established 2/7 single-agent MTD of 300 mg. The MTD will be determined as outlined in the protocol for each schedule. Following dose escalation, the sponsor has the option of expanding 1 or both schedules in order to establish the RP3D and schedule.

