### **5.1.3 DOSE-LIMITING TOXICITIES**

Subjects in both dosing schedules will be evaluated for DLTs according to the National Cancer Institute-Common Terminology Criteria for Adverse Events ([NCI-CTCAE](#)), Version 4.03 during the 28-day period of Cycle 1 combination therapy. Intrasubject dose escalation to the RP3D may be permitted once that dose has been determined and after a discussion has occurred between the treating physician and **the Sponsor's** study medical monitor. The decision to escalate to the next higher dose of oprozomib in **this** study will be based on an assessment of study drug-related DLTs during Cycle 1 by the CSRC. The CSRC consists of investigators, the **Sponsor's** study medical monitor, and **the Sponsor's** drug safety representative. Each subject in the cohort under review will be discussed and assessed. Once all data have been presented, the CSRC will decide on the most appropriate course of action regarding dose escalation based on guidance in [Section 5.1](#).

Study drug is defined as the combination of oprozomib, pomalidomide, and dexamethasone. Study drug-related is defined as a reasonable likelihood of clinical causality based on time of event, biology, dechallenge improvement and that the AE was not likely explained by the subject's clinical state, underlying disease, concomitant medication, or study/nonstudy procedure. Definition of DLTs and additional details are provided in [Section 10.5](#).

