### **5.1.4 SUBJECT REPLACEMENT**

Subjects must meet the following criteria to be considered evaluable for MTD determination during the 4-week DLT evaluation period unless a DLT occurs before the subject receives all planned doses of oprozomib for both the 5/14 and 2/7 dosing schedules:

- A minimum of 17 of 21 planned doses of pomalidomide must be received
- A minimum of 6 of 8 planned doses of dexamethasone must be received
- All planned doses of oprozomib must be received

Subjects not meeting all of the above criteria or assessed as unevaluable by the CSRC will be replaced.

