ANC $< 0.5 \times 10^9/L$	Hold dose a ; follow CBC at least 3 times per week; administration of colony stimulating factor b is permitted. Resume at full dose if ANC $\geq 0.5 \times 10^9/L$ within $< 7$ days. Resume at 1 dose decrement if ANC returns to $\geq 0.5 \times 10^9/L \geq 7$ days.	Hold dose a until ANC increases to $\geq 0.5 \times 10^9/L$ . Administer colony stimulating growth factor b . Resume at 1 dose decrement each subsequent decrease to $< 0.5 \times 10^9/L$ .

ANC = absolute neutrophil count; CBC = complete blood count.

a The maximum allowed dose interruption is 4 weeks for treatment-related toxicity.

b Colony stimulating factors such as filgrastim or sargramostim as examples.

Approved

Additional guidance regarding hematologic toxicities and dosing actions is as follows:

- To initiate a new cycle of pomalidomide, the neutrophil count must be at least 500 per  $\mu\text{L}$  and the platelet count must be at least 50,000 per  $\mu\text{L}$ . If toxicities continue to occur after dose reductions down to 1 mg, then discontinue pomalidomide.
- Nontreatment-related events: If the toxicity resolves to  $\leq$  Grade 1 or baseline and the toxicity is not treatment-related, oprozomib may be restarted at the same dose level
- If required by continued or recurrent toxicity, a second or third dose reduction of oprozomib may be permitted after discussion with the **Sponsor's** study medical monitor. No more than 3 dose reductions down to a minimum of 150 mg will be permitted for an individual subject on study and additional reductions will be managed by schedule change. If toxicity continues, oprozomib should be discontinued.

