Summaries that are displayed by system organ class and preferred terms will be ordered by descending order of incidence of system organ class and preferred term within each system organ class for the total group. Summaries of TEAEs, treatment-related AEs will also be provided by descending order of incidence of preferred terms in the total group.

All AEs, including TEAEs, will be included in listings by subject.

Listings of AEs determined to be DLTs during the first cycle of Phase 1, serious AEs, and AEs leading to discontinuation of study drug will be provided.

A summary of the number of deaths and the cause of death, classified by deaths within 30 days of last dose of study drug and deaths more than 30 days after the last dose, will be provided.

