7.8 Interim Analysis and Data Monitoring

The CSRC will review the clinical data of each dose cohort after three subjects have been treated for at least one cycle during phase 1 of the study. Based on the number of subjects with dose-limiting toxicity, escalation to the next higher OPZ dose may occur, the cohort may be expanded to six subjects, or dosing at that dose level may stop and the next-lower dose cohort may be expanded. The committee must agree that dose escalation to the next cohort is appropriate before it proceeds.

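### The Cycle 2 delay DLT cannot be established before Day 43, yet the evaluation window, the escalation rule and the SAP listing stay tied to Cycle 1

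*Protocol*

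**What the plan says.** Protocol Section 10.5 sets the window first: a DLT is a listed drug-related event "occurring within the 4 weeks after the first dose of combination therapy". One of the listed events is a delay to the Cycle 2 Day 1 dose, for which "drug-related toxicity persisting beyond 14 days from Cycle 1 Day 28 will be considered a DLT". The synopsis repeats both statements. The delay criterion does not say which drug's dose it means.

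The DLT count is then used in five places:

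- Protocol Section 5.1.4 sets the dosing minimums for a subject "to be considered evaluable for MTD determination during the 4-week DLT evaluation period". Every planned oprozomib dose is required unless a DLT comes first, and subjects who fall short are replaced.
- Protocol Section 5.1.3 says the decision to escalate "will be based on an assessment of study drug-related DLTs during Cycle 1 by the CSRC".
- Protocol Section 5.1 gives the rule: "As long as fewer than 33% of subjects experience a DLT in a given cohort, escalation will continue". The MTD needs fewer than 2 DLTs in 6 subjects.
- SAP Section 7.8 has the CSRC review a cohort "after three subjects have been treated for at least one cycle during phase 1 of the study", and the committee must agree before the dose goes up.
- SAP Section 7.6.1 plans "Listings of AEs determined to be DLTs during the first cycle of Phase 1".

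For the secondary point, Appendix A2 footnote j places the Cycle 1 blood counts on 2/7 on Days 1, 2, 8, 9, 15 and 16. Footnote t gives oprozomib on Days 22 and 23 as well.

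**The concern.** The definition conflicts with itself. If the four-week window governs, the delay criterion can never be met. If the criterion governs, which is the likelier intent, none of the rules that use the count has been adjusted to wait for it.

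DLT is the first-listed primary endpoint. It sets the MTD, and the RP3D may not exceed the MTD. A count that can still change after the committee has acted may put the next cohort on a higher dose too early, or leave a six-subject dose labelled tolerated when it fails the rule. The DLT listing may then also leave out the event that would show this.

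**Working it through.** **1. The plan's own figures.** Protocol Table 18 (SAP Table 1) follows from the 3+3 rule:

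- P(expand) = 3p(1−p)²
- P(tolerated) = (1−p)³ + 3p(1−p)² × (1−p)³

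At p = 0.33, P(expand) = 0.444 and P(tolerated) = 0.301 + 0.444 × 0.301 = 0.434, against 0.44 and 0.43 in the table. All twelve entries reproduce to two decimals. They assume that every DLT is known when the decision is taken.

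**2. Timing.** 28 + 14 = Day 42. Persistence beyond that means Day 43 at the earliest. 43 − 28 = 15 days after the window closes.

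**3. Effect of one unestablished delay DLT on the rule.**

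| Subjects | Count at Day 28 | Count at Day 43 | Effect |
|---|---|---|---|
| 3 | 0/3: escalate | 1/3 = 33.3% | not below 33%, so no escalation on three subjects |
| 6 | 1/6: tolerated | 2/6 | fails the rule of fewer than 2 in 6 |

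**4. Can it arise without an earlier DLT or replacement?** Yes, in a limited set of cases. Table 14 holds both drugs for painful Grade 2 neuropathy until Grade 1 or baseline, while the nonhematologic DLT threshold is Grade 3. If it starts before the last Cycle 1 oprozomib dose (Day 19 on 5/14, Day 23 on 2/7), a dose is missed and a subject without a DLT is not evaluable. If it starts later, all oprozomib doses have been taken. On 5/14, onset on Day 20 or 21 holds at most two pomalidomide doses. That prompts CSRC discussion, but 19 of 21 still exceeds the minimum of 17. From Day 22 on 5/14, or Day 24 on 2/7, no Cycle 1 oprozomib or pomalidomide dose is held at all. Section 10.4.1 allows toxicity holds of up to 4 weeks, so a delay past Day 42 is a foreseen course.

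Low platelets are a less clean example. The guidance under Table 13 says that for a new pomalidomide cycle "the platelet count must be at least 50,000 per" microlitre. Table 13's own Day 1 rows hold pomalidomide only below 30 × 10⁹/L and oprozomib only below 25 × 10⁹/L. Between 30 and 50 the two instructions for pomalidomide conflict, and oprozomib is not held. Whether that is a delay depends on the drug the criterion fails to name.

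**5. Secondary: counts on 2/7.** The last scheduled Cycle 1 count is Day 16. The next is Day 29, or Day 26 if drawn 72 hours early. An episode with onset s and length d meets no scheduled count if s ≥ 17 and s + d − 1 falls before the next count.

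- Next count Day 29: s ≤ 29 − d. For d = 7, onset on Days 17–22 is unseen (6 days). This falls by one for each extra day of length and reaches 0 at d = 13.
- Next count Day 26: s ≤ 26 − d. For d = 7, Days 17–19 (3 days), reaching 0 at d = 10.
- With a Day 22 count added, the free intervals are Days 17–21 (5 days) and 23–28 (6 days), both shorter than 7, so no such episode is missed.
- For comparison, 5/14 has its last count on Day 19. For d = 7, onset on Days 20–22 is unseen with a Day 29 draw, and none with a Day 26 draw.

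**The case against.** The strongest reply is that the CSRC discusses every subject, must agree before escalation, and would hardly overlook a subject who could not start Cycle 2. That is fair, and it is why the point says can and not will. It still leaves the decision to discretion in a design whose error rates in Table 18 presume a fixed rule.

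Second, escalating on 0/3 does not fix the MTD. The next cohort needs its own 28 days, so a Day 43 DLT in the lower cohort would be known 28 − 15 = 13 days before that window could close. This stands: for the MTD, only the last subjects of the final six are exposed. What remains at the three-subject step is that subjects may already be on the higher dose.

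Third, a toxicity persisting from Cycle 1 has its onset in the first cycle, so the SAP listing might capture it, and SAP Section 7.6.1 lists all AEs in any case. That also stands in part. The wording permits omission but does not compel it, and in the all-AE listing the event need not be marked as a DLT.

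Fourth, closing a subject's evaluation simply at Cycle 2 dosing would do harm. Grade 3 fatigue becomes a DLT only at 14 days, with full-dose oprozomib meanwhile, so an episode starting on Day 20 would be cut off at Day 29. This is right, and the fix allows for it.

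Fifth, the blood-count gap concerns silent, untransfused Grade 4 episodes in a narrow band of onset days, and Section 11.2 allows unscheduled counts. The Day 22 dose has a count exactly six days earlier, so only the Day 23 dose has none in its preceding six days. The point is minor.

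**Conclusion.** The inconsistency is real and should be fixed. As written, the CSRC can escalate, or call the last subjects of a six-subject cohort DLT-free, up to 15 days before a DLT that the protocol says counts is established. The decision effect is 0/3 in place of 1/3, or 1/6 in place of 2/6. This rests on reading the delay criterion as intended to count, and on toxicity that caused no missed oprozomib dose in Cycle 1.

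A reader might infer that a dose in OPZ007 was in fact escalated too soon, or that its MTD or RP3D is wrong. The documents do not support that: they report no Cycle 2 delays and no CSRC decision dates, and the RP3D also draws on data from several cycles. A reader might also infer that the Table 18 probabilities are off by some amount. The documents give no share of DLTs that are of the delay type, so no rate is claimed. Nor do they show that any thrombocytopenia was missed on 2/7. The gap is in the schedule of tests only, and it does not depend on the clinically-indicated wording of Amendment 3, which was not implemented.

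**What to change.** (a) In Protocol Sections 5.1.3, 5.1.4 and 10.5 and SAP Section 7.8, state that the delay criterion is an exception to the four-week window, and name the drug whose Day 1 dose defines the delay. A subject's evaluation closes at Day 28 or Cycle 2 Day 1 dosing, with two exceptions:

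- If drug-related toxicity is delaying Cycle 2, it closes at dosing, on the day toxicity stops being the reason (for example progression or withdrawal), or at Day 43 as a DLT.
- If a duration-based toxicity with Cycle 1 onset is unresolved, it closes when the duration criterion is met or the toxicity resolves.

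The CSRC escalates only on closed evaluations.

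(b) In SAP Section 7.6.1, list all DLTs over the DLT evaluation period. In the abbreviated study report, list every subject whose Cycle 2 Day 1 dose came after Day 42 or was not given, with the reason and the date of the CSRC decision.

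(c) Minor: on 2/7, add a pre-dose Day 22 blood count to Appendix A2 footnote j, at the visit already attended for vital signs. A Grade 4 platelet result would need repeat counts to establish its duration; Table 13 sets a repeat frequency for neutropenia but not for platelets.

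Items (a) and (c) are for a restarted or successor study only, because the program was terminated. Item (b) applies to OPZ007 and costs one phrase and one listing from existing dosing and committee dates. Prospectively, the cost is wording, one blood tube per 2/7 subject, and a wait of up to 15 days only when toxicity delays Cycle 2. For an unresolved duration-based toxicity the wait is shorter: Grade 3 fatigue starting on Day 28 completes 14 days on Day 41 (28 + 14 − 1), which is 13 days after Day 28.

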#### 10.4.1 DOSE REDUCTIONS

For this study, the initial cohort will start at an oprozomib dose level of 150 mg for the 5/14 schedule and 210 mg for the 2/7 schedule. For these subjects, oprozomib or pomalidomide or dexamethasone dose reductions are discouraged during the DLT assessments. Subjects requiring dose reductions in Cycle 1 will be referred to the CSRC for determination if the subject is considered evaluable and for DLT assessment per [Section 5.1.4](#). Dose reduction levels for oprozomib subsequent to Cycle 1 for the 5/14 and 2/7 dosing schedules are provided in [Table 9](#) and [Table 10](#), respectively. Modifications of the dose of oprozomib will occur in up to three 30-mg decrements down to a minimum dose of 150 mg. Additional reductions will be managed by schedule change.

Approved

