**Table 13 Guidelines for Dose Modification of Oprozomib/Placebo and Pomalidomide for Hematologic Toxicities**

Findings	Oprozomib	Pomalidomide
Findings on Day 1 of Cycle		
Recommended Action		
Platelets $< 25 \times 10^9/L$	Hold dose a until recovery $\geq 25 \times 10^9/L$ ; restart at previous dose.	Not applicable.
Platelets $< 30 \times 10^9/L$	Not Applicable.	Hold dose a , follow CBCs. Hold prophylactic anticoagulation until platelets return to $\geq 30 \times 10^9/L^a$ , then resume at 1 dose decrement.
ANC $< 0.5 \times 10^9/L$ or febrile neutropenia (fever $\geq 38.5^\circ C$ and ANC $< 1.0 \times 10^9/L$ )	Hold dose a . Add colony stimulating factor b With resolution to $\geq 1.0 \times 10^9/L$ , restart at previous dose.	Hold dose a . Add colony stimulating factor b With resolution to $\geq 0.5 \times 10^9/L$ , restart at 1 dose decrement.
Findings on Subsequent Days of Cycle		
Recommended Action		
Platelets 25 to $< 50 \times 10^9/L$ without $\geq$ Grade 2 bleeding/hemorrhage	Full dose.	Full dose.
Platelets 25 to $< 50 \times 10^9/L$ with $\geq$ Grade 2 bleeding/hemorrhage	Hold dose a until platelets return to $\geq 50 \times 10^9/L$ and/or bleeding is controlled, then resume at 1 dose decrement.	Hold dose a until platelets return to $\geq 50 \times 10^9/L$ and/or bleeding is controlled, then resume at 1 dose decrement.
Platelets $< 25 \times 10^9/L$ or thrombocytopenia with $\geq$ Grade 2 bleeding/hemorrhage	Hold dose a until recovery to $\geq 25 \times 10^9/L$ ; restart at 1 dose decrement.	Hold dose a . Hold prophylactic anticoagulation until platelets return to $\geq 30 \times 10^9/L^a$ , then resume at 1 dose decrement.
Neutropenic fever (ANC $< 1.0 \times 10^9/L$ and single temperature $> 38.3^\circ C$ or temperature $> 38.0^\circ C$ sustained for more than 1 hour)	Hold dose a ; follow CBC at least 3 times per week. Add colony stimulating factor b With resolution of fever and ANC $\geq 1.0 \times 10^9/L$ , restart at 1 dose decrement.	Hold dose a ; follow CBCs. Add colony stimulating factor b . With resolution of fever and ANC $\geq 1.0 \times 10^9/L$ , restart at 1 dose decrement.

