- h Subjects with urine positive for protein (> than trace) will need to collect a 24-hour urine sample for creatinine and protein analyses. Urine samples and urinalysis, done locally.
- i Full chemistry panel (sodium, potassium, calcium, alkaline phosphatase, blood urea nitrogen, uric acid, lactate dehydrogenase, creatinine, chloride, bicarbonate, glucose, total protein, albumin, total bilirubin, ALT, AST, phosphorous, and magnesium), done locally **if clinically indicated**. Calculate or measure creatinine clearance (CrCl). Screening results may be used for Cycle 1 Day 1 if obtained within 72 hours of Cycle 1 Day 1.
- j CBC and serum chemistry obtained on Days 1, 5, 15, and 19 of Cycles 1 and 2, and on Days 3 and 8 of Cycle 1. Day 1 samples for laboratory analyses can be drawn within 72 hours prior to dosing on Day 1 for all subsequent cycles after Cycle 1 **only if clinically indicated**.
- k Complete blood count (CBC) with differential, done locally, and includes the following: Hemoglobin, hematocrit, white blood cell (WBC) count with complete manual or automated differential (total neutrophils, lymphocytes, monocytes, eosinophils, basophils; reported as absolute counts), red blood cell (RBC) count, and platelet count. Screening results may be used for Cycle 1 Day 1 if obtained within 72 hours of Cycle 1 Day 1.

Approved

CONFIDENTIAL

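### The thrombocytopenia DLT criteria are out of severity order: a transfused Grade 3 event counts, but a short transfused Grade 4 event at 10,000 platelets or more without clinically significant bleeding does not

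*Protocol*

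**What the plan says.** Section 10.5 gives three limbs for a thrombocytopenia DLT, and the Synopsis repeats them:

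1. Grade 4 for 7 days or more.
2. Grade 4 for under 7 days, with either Grade 2 clinically significant bleeding or fewer than 10,000 "platelets requiring platelet transfusion, or" the third limb.
3. "Grade 3 with clinically significant bleeding or requiring platelet transfusion".

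Several other rules decide what happens to a subject whose event meets none of these:

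- **Section 10.5, CSRC bullet.** Toxicity that means a dose is reduced, or that either of the two drugs has to "be held in Cycle 1 that does not meet the criteria for DLT will be discussed by the CSRC". The two drugs are oprozomib and pomalidomide, and the committee decides whether the subject is evaluable.
- **Section 10.4.1.** "Subjects requiring dose reductions in Cycle 1 will be referred to the CSRC for determination if the subject is considered evaluable". The sentence goes on to mention DLT assessment, but refers to Section 5.1.4, which contains only evaluability criteria.
- **Section 5.1.4.** Absent a DLT, an evaluable subject needs at least 17 of 21 pomalidomide doses and 6 of 8 dexamethasone doses, and "All planned doses of oprozomib must be received". The consequence of falling short is then stated: "Subjects not meeting all of the above criteria or assessed as unevaluable by the CSRC will be replaced".
- **Table 13.** After Day 1 of a cycle, platelets below 25 x 10^9/L lead to a hold of both drugs. On recovery, the oprozomib instruction is "restart at 1 dose decrement".

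Section 5.1.3 has the CSRC discuss each subject in a cohort and decide on escalation. SAP Section 7.8 requires its agreement before the next cohort opens. The SAP has no DLT definition of its own.

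**The concern.** A DLT definition should be monotone in severity: if an event counts, the same event at a worse grade should count too. Here transfusion alone is enough at Grade 3. At Grade 4 for under 7 days it is enough only below 10,000 platelets. A wish to tolerate brief Grade 4 thrombocytopenia could explain leaving out untransfused cases, but it does not explain counting transfused Grade 3 and omitting transfused Grade 4.

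DLTs are a primary endpoint, and under Section 5.1 the DLT count decides whether a cohort escalates, expands or stops. A worse event that goes unscored can lower that count, either because the subject leaves the denominator or because the subject is tallied as DLT-free.

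**Working it through.** **The plan's own figures.** Protocol Table 18 follows from the ordinary 3+3 rule with true DLT rate p:

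- P(expand) = 3p(1-p)^2
- P(tolerated) = (1-p)^3 + 3p(1-p)^2 x (1-p)^3

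At p = 0.33, P(expand) = 3 x 0.33 x 0.67^2 = 0.444 (stated 0.44) and P(tolerated) = 0.434 (stated 0.43). All 12 cells of the table reproduce. The table is not in dispute. It confirms that one event matters by rule: scoring one more DLT moves 0/3 to 1/3 (expand) or 1/6 to 2/6 (not the MTD, which needs fewer than 2 in 6).

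**The three limbs applied to four cases.** The documents do not print the CTCAE platelet limits. Limb 2 adds the below-10,000 condition within Grade 4, so Grade 4 must include counts of 10,000 or more. The counts and durations below are illustrative.

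| Case | Limb 1 | Limb 2 | Limb 3 | DLT |
|---|---|---|---|---|
| Grade 3, 30,000, 2 days, transfused, no clinically significant bleeding | no | no | yes | yes |
| Grade 4, 8,000, 5 days, transfused, no such bleeding | no | yes | no | yes |
| Grade 4, 15,000, 5 days, transfused, Grade 2 such bleeding | no | yes | no | yes |
| Grade 4, 15,000, 5 days, transfused, no such bleeding | no | no | no | **no** |

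Limb 2 can be parsed in three ways: bleeding or (below 10,000 and transfused); (bleeding or below 10,000) and transfused; bleeding or below 10,000. The table is the same under all three.

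**Whether another rule in Section 10.5 scores the fourth case.**

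- The rule for any toxicity of Grade 3 or above is limited to nonhematologic events.
- The Cycle 2 delay rule needs toxicity persisting beyond 14 days from Day 28, that is past Day 42 (28 + 14). A Grade 4 phase of under 7 days that begins by Day 28 is over before Day 35 (28 + 7). Slow recovery could still trigger the rule in a particular subject, but the short episode does not do so by itself.
- The CSRC bullet settles evaluability, not DLT status.
- Limb 3 could be read as Grade 3 or higher, but the text does not say so. The same section writes the greater-or-equal sign for nonhematologic toxicity and for febrile neutropenia.

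**Where the subject goes instead.** This takes Grade 4 as falling below Table 13's 25 x 10^9/L cut-off, so that treatment is held.

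- *An oprozomib dose is missed.* Section 5.1.4 replaces the subject. Section 10.5 sends the same hold to the CSRC for a ruling on evaluability. The two sections are in tension on whether replacement is automatic.
- *Only pomalidomide is held, or a dose is reduced.* The CSRC rules on evaluability. Up to 4 pomalidomide doses can be missed within the threshold (21 - 17).
- *All dosing criteria are met.* The subject counts as DLT-free unless the CSRC calls the subject unevaluable.

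None of these routes records a DLT.

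**The case against.** The strongest defence is the CSRC. Section 5.1.3 puts every subject in the cohort before it, and it can decline to escalate. A transfused Grade 4 subject with drug held is unlikely to pass unnoticed. That stands as mitigation. It does not amend Section 10.5, so the event still does not enter the DLT count.

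The below-10,000 condition may also be deliberate, to keep DLTs from depending on local practice, since Section 10.6.2 leaves platelet transfusion to institutional guidelines. But limb 3 already accepts that dependence at Grade 3. The order could instead be restored by narrowing limb 3. That would be consistent too, but it would drop events the plan now counts, so widening is the safer repair.

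A reader might infer three stronger things, and the documents support none of them:

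- *That affected subjects are routinely replaced because blood counts fall on dosing days.* Appendix A1 has "CBC and serum chemistry obtained on Days 1, 5, 15, and 19 of Cycles 1 and 2", and several of these are oprozomib days. But nothing in the footnotes on Cycle 1 blood counts requires the result before that day's dose, and Section 11.2 allows unscheduled samples. The schedule does not show which route is usual.
- *That DLTs in other oprozomib studies show the gap will be hit.* Sections 3.4.2.2 and 3.4.2.3 report Grade 4 thrombocytopenia as a DLT, but not those studies' DLT definitions, nor the duration, bleeding or transfusion. Those events might have been DLTs here as well.
- *That the MTD found in this study is too high.* Neither document reports a gap case or gives its frequency.

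**Conclusion.** The inversion is real on the text, identical in Section 10.5 and the Synopsis, and not closed by any other DLT rule. Where it operates, its direction is toward fewer counted DLTs. Its size cannot be stated, because that needs an event frequency the documents do not give, and none is claimed.

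The severity is minor. The gap is narrow and CSRC review limits the consequence. SAP Section 2.1 describes Part 1 as completed, and the note at the front of the protocol says Amendment 3 was not implemented, so an edit now would not change a past escalation decision. What remains is the reading of the reported DLTs and MTD, and any later protocol that reuses the definition.

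The conclusion rests on reading Grade 3 in limb 3 as Grade 3 only. The routing through treatment holds also assumes that Grade 4 lies below Table 13's cut-off.

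**What to change.** In Section 10.5 and the Synopsis, keep limb 1 (Grade 4 for 7 days or more) and replace limbs 2 and 3 with one limb: *Grade 3 or higher with clinically significant bleeding (Grade 2 or higher) or requiring platelet transfusion*. This makes the below-10,000 condition and the separate Grade 4 bleeding condition unnecessary. Limb 3 currently gives no bleeding grade, so if the sponsor would treat some Grade 1 bleeding as clinically significant, the parenthesis should be left out.

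The edit is one limb in two places. It may add a few DLTs and make the MTD slightly more conservative, with some dependence on site transfusion practice, which limb 3 already accepts for Grade 3.

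No SAP change is needed. SAP Sections 7.1, 7.6.1 and 7.6.2 already list eCRF, adverse event and laboratory data by subject. A flag for any Cycle 1 transfused Grade 4 subject not scored as a DLT, with replacement status, would be an optional convenience.
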